#### 5.3 Secondary Endpoint Analyses

The following endpoints comprise the secondary endpoints and the time points that each will be assessed:

- Responder Rate at 7 days, 30 days, and 6, 12, 18 and 24 months;
- Frequency of procedure-related adverse events (non-serious and serious), assessed at the index procedure and through the 7-day, 30-day, 3-month, 6-month, 12-month, 18-month, and 24-month follow-up time points;
- Frequency of device-related adverse events (non-serious and serious), assessed at the index procedure and through the 7-day, 30-day, 3-month, 6-month, 12-month, 18-month and 24-month follow-up time points;
- NOSE score, change from baseline, to the 7-day, 30-day, 3-month, 6-month, 12-month, 18-month, and 24-month follow-up time points;
- Visual Analogue Scale (VAS), change from baseline, to the 7-day, 30-day, 3-month, 6-month, 12-month, 18-month, and 24-month follow-up time points;
- Endoscopic lateral wall insufficiency (LWI) score as assessed by independent reviewers, change from baseline to the 3-month and 6-month time points;
- Epworth Sleepiness Scale (ESS) score and Pittsburg Sleepiness Quality Index, change from baseline, to the 7-day, 30-day, 3-month, 6-month, 12-month, 18-month, and 24-month follow-up time points.

All secondary endpoints will be assessed for the Sham Control Arm at two additional visits. The Sham arm will have follow-up visits at 7 days, 30 days, and 3 months after the initial

### STATISTICAL ANALYSIS PLAN

treatment/randomization, and 30 days, 3 months, 6, months, 12 months, 18 months, and 24 months in subjects that cross over.

A 2-sided binomial test of proportions will be used to compare treatment groups for binary endpoints. A two-sample t-test will be used for continuous endpoints.

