#### 2.1 Design, Treatments and Visits

This clinical study is to evaluate the performance of the device in comparison to no intervention, in this case, a "sham treatment". The study design and methods have been developed using input from previous and ongoing studies with the Latera Implant. This randomized, single-blind, sham-controlled, multicenter study of the Latera Nasal Absorbable Implant will enroll subjects with nasal valve collapse due to or primarily due to insufficient cartilaginous support of the lateral nasal wall into one of two treatment arms, a) implantation with the Latera device or b) Sham Control.

There are three treatment arms:

Latera Treatment Arm

Subjects in the active treatment arm will receive the Latera Implant, a PLLA-PDLA copolymer, delivered to the region of the lateral nasal wall cartilages to provide support. It is placed using standard, minimally invasive techniques and is absorbed over a period of approximately 18 months.

ST 800-A

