#### **Crossover Subjects**

Subjects will be unblinded after the 3-month assessment is complete. For subjects in the Sham Control arm, the subject will be treated with the Latera Implant if they still meet all eligibility criteria. The subject's data will continue to be recorded thereafter through 24 months post-implant. If the subject does not meet the eligibility criteria, he/she will exit the study.

For subjects randomized to the Latera Implant arm, the follow-up evaluations will be at 7 days, 30 days, 3 months, 6 months, 12 months, 18 months, and 24 months post-procedure. For subjects randomized to the Sham Control arm, the follow-up evaluation will be at 7 days, 30 days, and 3 months.

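### SAP 5.3 sets no time limit and no cross-over rule for its between-group tests, and from 6 months on no such test can estimate Latera against sham

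*SAP*

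**What the plan says.** SAP 5.3 lists the secondary endpoints with their time points, for example "Responder Rate at 7 days, 30 days, and 6, 12, 18 and 24 months". NOSE, VAS, the two sleep scales and the two adverse event frequencies also run to 24 months; the lateral wall insufficiency (LWI) score runs to 6 months. The section closes with two test sentences: "A 2-sided binomial test of proportions will be used to compare treatment groups for binary endpoints" and "A two-sample t-test will be used for continuous endpoints". Neither is limited to certain visits, and neither mentions cross-over.

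On sham follow-up, SAP 2.1 says "For subjects randomized to the Sham Control arm, the follow-up evaluation will be at 7 days, 30 days, and 3 months". Under SAP 4.2 every subject is unblinded once the 3-month assessment is done. Sham subjects who still qualify may then be implanted, with the visit schedule restarted (Protocol 5.3). For the others, "If the subject does not meet the eligibility criteria, he/she will exit the study"; Protocol 5.3 also exits those who decline to go on.

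The grouping of cross-over subjects is described in different ways:

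- SAP 2.1 first describes two arms, then says "There are three treatment arms" and lists Crossover Subjects as the third.
- Protocol 5.3 has sham subjects cross over into the Latera arm.
- SAP 5.3 credits the repeat visits to the sham arm: "All secondary endpoints will be assessed for the Sham Control Arm at two additional visits". It gives that arm's later visits as "and 30 days, 3 months, 6, months, 12 months, 18 months, and 24 months in subjects that cross over".
- The Protocol synopsis gives the Sham Control group 27 months of follow-up.

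**The concern.** Read as written, the test sentences cover every endpoint and time point listed above them. From 6 months on there is no scheduled follow-up of un-implanted sham subjects, so a test labelled Latera versus Sham would not measure what its label says.

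The late results are the trial's evidence on durability and most of its device safety record. If cross-overs are kept under Sham, an effect that persists in both groups could be reported as no difference, and device events in implanted people could be counted as sham events. Because the SAP does not settle the grouping, the choice could be made after the data are seen.

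**Working it through.** **Does another section supply the rule?** No.

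- SAP 4.1.1 analyses subjects by procedure received, but only after mis-randomisation.
- SAP 4.2 excludes subjects from the per-protocol dataset, but only for unblinding before 3 months.
- Protocol 5.3 refers to Section 6.2 for the analysis consequences, and 6.2 says nothing about cross-overs.

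**What a test at 6 months or later would compare**

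| Cross-overs treated as | Textual basis | Late comparison |
|---|---|---|
| (a) a third group | SAP 2.1 | No sham data. Latera v cross-over can be run, but it is not a sham contrast |
| (b) part of the Latera arm | Protocol 5.3 | No comparator |
| (c) part of the sham arm | SAP 5.3; Protocol synopsis | Randomised Latera v selected, unblinded, implanted subjects |

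There is one narrow exception. Subjects unblinded before 3 months are recorded to 24 months, so a few un-implanted sham subjects might have later data. SAP 4.2 removes them from the per-protocol dataset.

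**How many comparisons.** Count each endpoint and time point once, with ESS and PSQI separate and each adverse event frequency as one.

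- Index procedure: 2.
- 7 days: 7. 30 days: 7. 3 months: 7 (the 3-month responder rate is the primary endpoint and is left out).
- 6 months and later: responder rate 4, procedure events 4, device events 4, NOSE 4, VAS 4, LWI 1, ESS 4, PSQI 4 = 29.
- Total: 2 + 7 + 7 + 7 + 29 = 52. Without adverse events, 21 of 36 are late.

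**The plan's own figure.** The SAP gives no figure for the late tests. The nearest is 124 evaluable subjects for 90% power. Simulating looks at 22, 60 and 124 with the tabulated boundaries gives a one-sided type I error of 0.0251 and power of 90.2% (unpooled variance) or 87.3% (pooled). That figure is not in dispute; it supplies 124/2 = 62 per arm.

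**Responder rate under (c).** The expected difference is the Latera rate minus the cross-over rate; no sham rate enters. The documents do not give the number crossing over or the late response rates. Assume 50 to 62 Latera subjects, 20 to 62 cross-overs, Latera at 70%, and a two-sided 5% pooled z-test enumerated exactly:

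| Cross-over rate | Probability of rejecting |
|---|---|
| 70% | 4.8% to 5.6% |
| 60% | 12.5% to 21.5% |
| 80% | 11.8% to 26.2% |
| For reference: true 70% v 40%, 62 per arm | 93.6% |

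The first row is simply the test's nominal error. It shows that the test says nothing about sham. The upper limit of 62 cross-overs needs every sham subject to requalify, consent and be implanted. A sham responder can still requalify (NOSE falling from 100 to 80 is a 20% reduction and remains above 55), but 62 is an extreme.

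**Device events under (c).** Expected events moved under Sham = number of cross-overs × rate. Take 31 to 62 cross-overs (an assumption) and the three prior studies in Protocol 1.2:

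- LATERAL OR: 6/113 = 5.3%, giving 1.6 to 3.3.
- LATERAL Office: 15/165 = 9.1%, giving 2.8 to 5.6.
- German study: 4/30 = 13.3%, giving 4.1 to 8.3.

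The two US figures are events over subjects treated, so they are upper limits on the per-subject rate in the data reported so far. Those data are preliminary. The German study used the predecessor device.

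**The case against.** The documents never claim a sham-controlled effect beyond 3 months. The primary endpoint is at 3 months, the effectiveness conclusion rests on that test, and unblinding and cross-over are openly described. The SAP does not order each late test by name, and these analyses are not confirmatory. All of this stands and limits the weight of the point. It does not remove it, because the test sentences as written still reach the late visits.

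The harm also depends on the grouping. Only (c) can show a persisting effect as no difference; (b) leaves descriptive summaries, and (a) permits a test that is at least not labelled Sham. This stands too. It is a reason for the SAP to choose.

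A reader might go further and infer that the 30-day and 3-month sham data are diluted, because sham subjects who cross over attend those visits twice. The documents do not support that. SAP 5.3 separates visits after randomisation from visits after cross-over, SAP 4.2 restarts follow-up at implant, and SAP 2.1 lists Crossover Subjects on their own. The natural reading is the post-sham record, and no passage directs that both records enter one arm. What remains is a wording gap: 5.3 credits the repeat visits to the sham arm without saying which record is used. Adverse events have a similar gap, since Protocol Table 2 records them at the cross-over procedure as well as at the index procedure.

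A reader might also infer that the secondary analyses have no population at all. Section 5.3 names none, but the SAP 4.2 exclusion implies a per-protocol dataset for secondary endpoints.

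**Conclusion.** The point holds for visits at 6 months and later. On any grouping of cross-over subjects, a between-group test there does not estimate Latera against sham. By the count above this is 29 of 52 secondary comparisons.

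That conclusion follows from the text alone. The rejection rates and event counts are illustrations for grouping (c) and rest on the assumed cross-over numbers and response rates; they do not show that the late tests must find no difference. At 30 days and 3 months only a clarification is needed. The primary endpoint, its test and the sample size are untouched. The change is worth making before late data are examined, because it closes an open analysis choice at almost no cost.

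**What to change.** In SAP 5.3:

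- Limit between-arm tests to the index procedure and visits through 3 months after randomisation, using only pre-cross-over data for the sham arm.
- At 6 to 24 months, report the randomised Latera arm alone, with confidence intervals.
- Report cross-overs separately, as open-label data on post-implant time, and state the baseline. Protocol Table 2 has NOSE, VAS, ESS and PSQI at cross-over screening but no video. Subjects are selected on NOSE at requalification, so change from that visit is open to regression to the mean.
- Tabulate adverse events from the cross-over procedure onward by actual device exposure, not under Sham.
- Name the analysis population for secondary endpoints, in line with SAP 4.2.

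The cost is SAP wording, with no extra visits or data. The late between-arm p-values are dropped.

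Separately, and as an improvement rather than the correction of an error, NOSE, VAS, ESS and PSQI through 3 months could be analysed by ANCOVA with the baseline score as covariate instead of a t-test on change. With baseline SD s0, follow-up SD s1 and correlation r, the variance ratio is s1²(1 − r²)/(s0² + s1² − 2·r·s0·s1). For r from 0.3 to 0.7 it is 0.65 to 0.85 with equal SDs, 0.87 to 1.00 if s1 = 1.5·s0, and 0.93 to 1.00 if s1 = 2·s0. The documents give neither r nor the SDs, so the gain may be small.

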2. STUDY DEVICE

This is a Non-Significant Risk ("NSR"), post-marketing study and will be conducted in accordance with the requirements prescribed in 21 CFR §812.2(b). Because it is a post-market evaluation of a 510(k) cleared medical device in commercial distribution, used according to FDA cleared indications for use, investigational device labeling described under §812.2(b) is not required. The choice of conducting this study under §812.2(b) represents a conservative approach as the study could otherwise have been categorized as Exempted per §812.2(c).

This evaluation of the Spirox Latera Absorbable Nasal Implant and Delivery Device is considered a NSR device study for the following reasons:

- While the device is an Implant, it does not present a potential for serious risk to the health, safety, or welfare of a subject;
- The device is not purported or represented to be used for supporting or sustaining human life;
- The device is not intended for a use of substantial importance in diagnosing, curing, mitigating, or treating disease or otherwise preventing impairment of human health; and,
- The device does not otherwise present a potential for serious risk to the health, safety or welfare of the subject.

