 - iii. In addition, anesthesia may be injected along the proposed implantation track, starting at the alar rim and progressing to the supra-periosteal region of the maxilla. Additional injections into alar rim may also be considered.
 - d. Wait approximately 10 minutes for anesthesia to be in full effect.
- 6. RANDOMIZATION: Subjects are randomized into the Sham Control Arm or the Latera Implant Treatment Arm, after anesthetic is delivered. Treatment assignment will remain blinded to the study subject.
- In the event the subject is selected for the Latera Implant Arm, the implants (bilateral) will be delivered in a loaded delivery tool, using standard deployment technique per Spirox IFU (Attachment C). Only one Implant per side may be placed.
- 8. In the event the subject is selected for the Sham Control Arm, follow the exact same process for implant delivery per Spirox IFU (**Attachment C**), including pulling the alar rim back allowing insertion of the cannula of an unloaded (no implant) delivery tool. No implant is deployed in the Sham Control Arm.

The following data will be recorded on the subject's procedure CRF:

- Anesthesia regimen
- Photograph image with Trajectory Plan
- The Randomization Assignment
- All medication administered pre- and post-procedure.
- Implant placement or sham control logistical information
- Any adverse events or adverse device effects observed during this visit will be collected and documented.

Data collected for the Treatment Visit should be entered into the EDC no later than five (5) business days after the completion of procedure/visit.

IMPORTANT: Prior to discharge, provide the post-procedure reminder form and instructions for managing the post procedure recovery time. In addition, a course of antibiotics (e.g. Amoxicillin, Augmentin or equivalent) may be prescribed by the physician pursuant to local practice standards. Upon completion of the treatment visit, the subject will be scheduled for their next Follow-Up Visit.

Note: Space intentionally left blank.

Table 2. Schedule of Study Activities

Visits (± Windows)	Screening/Baseline	Index Procedure - Day 0	Visit $3 - 7 \pm 2$ days	Visit 4 - 30 ± 7 days*	Visit 5 - 90 ± 14 days*	Cross-Over Screening (for Sham Control Subjects only)	Cross-Over Procedure (for Sham Control Subjects only)	Visit $6 - 6$ month ± 14 days	Visit $7 - 12$ months ± 30 days	Visit $8 - 18$ months ± 30 days	Visit $9 - 24$ months ± 30 days
Informed Consent	Х					Х					

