8. RISK-BENEFIT ANALYSIS

8.1. Risks to the Subjects

The list below described the general types of potential risks to the study subjects.

Adverse Events
Infection
Inflammation
Pain or discomfort
Serous wound drainage
Hematoma
Ecchymosis
Extrusion
Retrieval
Foreign body reaction
Foreign body sensation
Device Fracture
Device Malposition or Migration
Device Palpable
Skin Irritation
Allergic reaction to device
Allergic reaction to medications from procedure or follow up
Allergic reaction to any study related medications
Hematoma*, general (such as cannula insertion, delivery of anesthetics, manipulation of nose during procedure, etc.)
Perceptible cosmetic changes
Respiratory / sinus infection or rhinorrhea
Continued or worsened breathing symptoms
Scarring
Firmness, swelling, redness
Decreased sense of smell

*Includes hematoma from cannula insertion, delivery of anesthetics, manipulation of nose during procedure)

There are other health risks and discomforts associated with the testing that the subjects will undergo before and after their procedure, including but not limited to pain and bruising at the implant pierce point site or areas of anesthetic injections.

For subjects in the Sham Control Group, the use of anesthetic and insertion of the cannula imparts the same risks except for those directly attributable to an implant, without the potential benefit of the treatment.

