An adverse device effect (ADE) is any unwanted and unintended response to a medical device. This definition includes any event resulting from insufficiencies or inadequacies in the instructions for use or the deployment of the device and any event that is a result of user error. A serious adverse device effect (SADE) is an adverse device effect that has resulted in any of the consequences characteristic of a serious adverse event or that might have led to any of the consequences if suitable action had not been taken or intervention had not been made or if circumstances had been less opportune. An unanticipated adverse device effect (UADE) is defined as "any serious adverse effect on health or safety or any life-threatening problem or death caused by, or associated with, a device, if that effect, problem, or death was not previously identified in nature, severity, or degree of incidence in the investigational plan or application (including a supplementary application), or any other unanticipated serious problem associated with the device that relates to the rights, safety, or welfare of subjects."

Section 8.1 includes a list of possible adverse events associated with nasal interventions. These events are considered reportable at all time points throughout the trial and require submission to the Sponsor within 1 business day of receipt of information. It is recognized that adverse events may not be reported by the study subject until their follow up visits due to the low risk nature of the potential events.

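### SAP 5.3 tests device-related and procedure-related adverse events separately between arms, although sham has no implant before month 3 and no rule assigns shared procedural events to device, procedure or both

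*SAP*

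**What the plan says.** SAP 5.3 lists "Frequency of procedure-related adverse events (non-serious and serious), assessed at the index procedure" and, as a separate item, "Frequency of device-related adverse events (non-serious and serious), assessed at the index procedure". Both run through 24 months. After the list comes a single rule for comparisons: "A 2-sided binomial test of proportions will be used to compare treatment groups for binary endpoints". AEs are not exempted. The SAP does not say whether frequency is counted per subject or per event, so the rule reaches the AE endpoints by implication. SAP 5.4.1 leaves AEs and SAEs out of its summaries by treatment, and no other SAP section is devoted to AE analysis.

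On exposure, Protocol 5.2 describes the sham procedure as "allowing insertion of the cannula of an unloaded (no implant) delivery tool" and adds "No implant is deployed in the Sham Control Arm". SAP 4.2 bars an implant in sham subjects until the 3-month assessment is done; eligible sham subjects may receive one after that. Protocol 8.1 says of the sham group that "the use of anesthetic and insertion of the cannula imparts the same risks except for those directly attributable to an implant".

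On classification, Protocol 9.1 sets one four-level relatedness scale for device and for procedure. Protocol 9.2 lets an event be related to either or both. Protocol 9.3 has a Medical Monitor classify every event and prevail over the site in a conflict.

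**The concern.** The randomised comparison can estimate how much harm the implant adds to a procedure that both arms undergo. Neither planned test does this.

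The device test includes events that need an implant: extrusion, retrieval, fracture, migration. For these the sham rate is zero by construction up to month 3, so a p-value against sham tells the reader nothing about them.

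The procedure test depends on coding. Haematoma, infection and pain can follow the cannula or the anaesthetic in either arm. The documents do not say when such an event is coded device, procedure or both. The trial is single-blind with only the subject masked, so the site knows the arm, and nothing says that the Medical Monitor does not. Device coding of such event types has a precedent: the initial German study counted a haematoma and an inflammation among its device-related events (Protocol 1.2). Any shared event that is coded device-only in a Latera subject drops out of the Latera procedure rate, while the sham rate keeps its counterpart. The procedure endpoint could then show an apparent safety advantage for Latera that comes from coding.

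The 24-month horizon adds a further problem. Once sham subjects cross over or exit after month 3, there is no implant-free comparator.

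**Working it through.** **Inputs.** The plan gives no figure for the AE comparisons. Its maximum of 124 evaluable subjects at 1:1 gives 62 per arm. That figure is consistent with the plan: simulating the stated boundaries at 22, 60 and 124 (unpooled variance) gives power 0.9015 and cumulative type I error 0.0005, 0.0093 and 0.0251, against 90% and 0.0005, 0.0093 and 0.0250 stated. The SAP gives no significance level for secondary endpoints and no formula for this test, so I assume two-sided 0.05 and show both pooled z and Fisher's exact test.

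**Device test with sham at 0/62.** For x Latera subjects with an event, the difference is x/62, the pooled proportion is p = x/124, and SE = √[p(1−p)(2/62)].

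- x = 3: difference 0.0484, SE 0.0276, z = 1.75, p = 0.080.
- x = 4: difference 0.0645, SE 0.0317, z = 2.03, p = 0.042.
- Fisher: x = 5 gives p = 0.058; x = 6 gives p = 0.028.

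Pooled z therefore needs 4 Latera subjects and Fisher needs 6. The thresholds are the same at 30 or 75 per arm. The chance of reaching them at 62 per arm, by true Latera rate:

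| Latera rate | Source in Protocol 1.2 | Pooled z | Fisher |
|---|---|---|---|
| 2.2% | Table 1, 5/223 | 5% | 0.2% |
| 4.4% | Table 1, 14/317 | 29% | 5% |
| 13.3% | Initial study, 4/30 | 97% | 85% |

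The first two denominators are those of the per-implant retrieval rates, so these rows are a range and not per-subject estimates.

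**Procedure test with no true difference.** Let q be the proportion of subjects in each arm with a shared procedural event, and f the fraction of those in the Latera arm coded device-only. The recorded procedure-related rate is q(1−f) in Latera and q in sham. At q = 10% and f = 50% that is 5% against 10%. The chance of a false result for Latera is the sum of Bin(i; 62, q(1−f)) × Bin(j; 62, q) over all i < j with p < 0.05. Results are pooled z / Fisher:

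| q | f = 0 | f = 25% | f = 50% | f = 75% |
|---|---|---|---|---|
| 10% | 2.5% / 1.1% | 7% / 3% | 18% / 9% | 41% / 24% |
| 20% | 2.4% / 1.5% | 10% / 7% | 34% / 26% | 74% / 65% |
| 30% | 2.5% / 1.6% | 15% / 11% | 52% / 44% | 92% / 88% |

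The column f = 0 also covers dual coding, where every shared event counts as procedure-related whatever else it is.

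**Combined endpoint.** Count a subject once for any device- or procedure-related event. If a fraction d of Latera subjects has an implant-specific event, independently of shared events, the Latera rate is q + d(1−q), the sham rate is q, and the excess is d(1−q). The split f does not appear. With d = 0 the chance of a false result for Latera is 2.4 to 2.7% (pooled z) or 1.1 to 1.7% (Fisher) for q from 10 to 40%.

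**The case against.** A reader might infer three stronger things. The documents do not support them.

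- **That AE scoring has no common basis.** Protocol 9.1 to 9.3 sets one scale for both arms and one classifier whose judgement prevails. What is missing is narrower: the rule for device, procedure or both; which scale levels count as related; and whether the classifier is masked.
- **That the device test is decided before the trial starts.** Only the direction is fixed, and only for implant-specific events; the table above shows significance anywhere from 0.2% to 97%. Nor are device-related events excluded in sham. Protocol 2 says "This evaluation of the Spirox Latera Absorbable Nasal Implant and Delivery Device is considered a NSR device study", sham subjects are exposed to the delivery tool, and Protocol 9.1 says of an adverse device effect that "This definition includes any event resulting from insufficiencies or inadequacies in the instructions for use or the deployment of the device". A haematoma from the sham cannula could be rated device-related.
- **That the procedure test will favour Latera.** This needs device-only coding of shared events. Protocol 9.2 permits dual coding, which removes the bias, and the AE form in Attachment F, which is not reproduced, may ask for both ratings. No document gives a procedure-related rate or a coding split.

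It is also fair to say that the only formal hypothesis is the primary one, that no AE p-value has a success criterion, and that SAP 5.1 promises descriptive statistics for all data points, with between-arm differences and intervals as an option.

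All of this stands, and it limits the point without removing it. Dual coding is allowed but not required, a difference with its interval is optional, and no planned comparison combines the two categories or stops at month 3.

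**Conclusion.** The concern holds in a limited form. As written, SAP 5.3 applies a between-arm test to device-related AEs, and for the implant-specific ones the sham arm cannot contribute before month 3; that p-value is uninformative in direction, though not certain to be significant. The procedure test is open to a bias towards Latera whose size depends on coding that the plan leaves unstated. It is nil with dual coding. With half of shared Latera events coded device-only and shared rates of 10 to 30%, the chance of a false result for Latera is 18 to 52% (pooled z) or 9 to 44% (Fisher).

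These figures rest on 62 per arm (the analysis set for AEs is not stated), a two-sided 0.05 level, per-subject counting, and assumed values of q and f. The structural conclusion does not need them: neither split test estimates the excess harm of implant over sham, and after month 3 there is no implant-free arm to compare with.

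**What to change.** In SAP 5.3:

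1. Make the between-arm safety comparison the proportion of subjects with any device- or procedure-related AE from the procedure to the 3-month visit, before any crossover implant, with the difference and its 95% CI. State which relatedness levels count as related.
2. Report device-related AEs descriptively in implanted subjects, with an exact 95% CI and no test against sham. This includes events after month 3 and after crossover.
3. Keep the procedure-related rate as a descriptive split.
4. Add a summary by arm of all recorded AEs regardless of relatedness. The combined endpoint does not depend on the device/procedure split, but it does not protect against an unmasked classifier calling the same event related in one arm and unrelated in the other. This summary is limited to the events recorded, because Protocol 9.2 requires capture only of related ones.

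The cost is SAP wording and one derived variable from data already collected. The drawback for the sponsor is that the headline AE rate for Latera will usually be higher than either split rate.

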This Clinical Investigational Plan (CIP), informed consent forms (ICF), recruitment materials, and all participant materials will be submitted to the Institutional Review Board (IRB) for review and approval. Approval of the CIP and the ICF must be obtained before any subject is enrolled. Any amendment to the CIP will require review and approval by the IRB before the changes are implemented to the study. In addition, all changes to the ICF will be IRB-approved and a determination will be made regarding whether a new consent needs to be obtained from subjects who previously provided consent.

INVESTIGATOR SIGNATURE PAGE

Investigator Name

Title

Site Name

Site Number

Date

I have read the protocol and agree that it contains all necessary details for carrying out this study. I will conduct the study as outlined therein.

I agree to keep records on all subject information (e.g., source documents and informed consent forms), device shipments and return forms, and all other information collected during the study, in accordance with local and national regulations.

Investigator Signature

SYNOPSIS

Study Title	Latera RCT – Latera [®] Absorbable Nasal Implant vs. Sham Control for Lateral Nasal Valve Collapse		
Spirox Protocol Number	CP04		
Investigational Device	Spirox Latera Absorbable Nasal Implant		
ClinicalTrials.gov Identifier	NCT 03400787		
Sponsor	Spirox, Inc. [name]		
Study Purpose	To evaluate the Latera Absorbable Nasal Implant (Latera Implant) Implant versus Sham Control in subjects with nasal valve collapse due to or primarily due to insufficient cartilaginous support of the lateral nasal wall		
Objective	The primary objective of the LATERA RCT is to demonstrate the superiority of the Latera Implant to improve nasal breathing, compared with a Sham Control treatment.		
Phase of Study	Post-market		
Study Design	Randomized (1:1), sham-controlled, single-blind, multicenter pos market trial using an adaptive trial design		
Investigational Sites	Up to 15 investigational sites in the United States, in office-based locations with investigators experienced in standard nasal interventions for airway obstructions and the use of the Latera Implant		
Study Population	The Adaptive Design allows for enrollment of up to 150 subjects with nasal airway obstruction due to or primarily due to nasal valve collapse.		

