#### 2.4 Sample Size Considerations

The primary analysis will be based on a 1-sided binomial test of proportions. Assuming a Sham Control response rate of 40% and a Latera Treatment response rate of 70% at month 3, a maximum sample size of 124 evaluable subjects is required for 90% power and preserving a 2.5% (one-sided) type I error rate. This study is designed as a group-sequential trial with 2 interim analyses and a final analysis. The stopping boundaries are derived using the Triangular

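### SAP 5.3 tests changes from baseline in NOSE, VAS, ESS and PSQI by a t-test without baseline as a covariate; ANCOVA would generally be more precise at almost no cost

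*SAP*

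**What the plan says.** SAP 5.3 lists the continuous patient-reported endpoints as change scores: "NOSE score, change from baseline, to the 7-day, 30-day, 3-month, 6-month, 12-month, 18-month, and 24-month follow-up time points", then "Visual Analogue Scale (VAS), change from baseline, to the 7-day" and later visits, and "Epworth Sleepiness Scale (ESS) score and Pittsburg Sleepiness Quality Index, change from baseline" over the same visits. The only method given for them is "A two-sample t-test will be used for continuous endpoints". No covariate or repeated-measures model is named there, and the protocol names no other method.

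Baseline scores appear in two other places, and neither adjusts these treatment effects:

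- SAP 5.4.1 compares baseline variables between arms.
- SAP 5.5 uses baseline NOSE, VAS and ESS as covariates, but only to impute the primary responder endpoint.

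The design is "Randomized (1:1), sham-controlled, single-blind" (Protocol, Synopsis). Protocol 5.2 describes site-specific assignments and mentions no stratification by symptom score. Under SAP 4.2 all subjects are unblinded after the 3-month assessment, and eligible sham subjects may then receive the implant.

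**The concern.** A change score gives each subject's baseline a coefficient of exactly 1. The true regression slope of follow-up on baseline need not be 1. When it is not, two things follow. The treatment difference has a larger variance than it needs. And part of any chance baseline difference between the arms stays in the estimate.

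The comparisons affected are those at 7 days, 30 days and 3 months. After that there is no concurrent sham arm, so these visits are the trial's only sham-controlled evidence on the size of the symptom effect and on sleep. The sample is small: at most 124 evaluable subjects by design, and fewer if the trial stops early. All four scales are recorded at baseline for every subject (Protocol 5.1 and Table 2), so the information that would sharpen the estimate is already there.

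**Working it through.** **The plan's own figure.** The documents give no SD, correlation, power or sample size for the continuous endpoints. The only sizing figure is for the binary primary endpoint. With responder rates of 40% under sham and 70% under Latera, SAP 2.4 states that "a maximum sample size of 124 evaluable subjects is required for 90% power". It reproduces. A fixed design needs 56 per arm. A simulation of the three looks at 22, 60 and 124 with the tabulated boundaries gives 90.2% power and cumulative one-sided type I error of 0.0251. So 62 per arm is a sound basis for what follows.

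**Formulas.** Let sb and sf be the baseline and follow-up SDs, r their within-arm correlation, and b = r·sf/sb the slope.

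- Variance per subject, change score: sb² + sf² − 2·r·sb·sf
- Variance per subject, ANCOVA: sf²(1 − r²)
- Shift of the change-score estimate for baseline difference d (Latera minus sham): (b − 1)d

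**Equal SDs** (assumption). The variance ratio is (1 − r²)/(2 − 2r) = (1 + r)/2.

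| r | ratio | variance saved | subjects for ANCOVA to match a t-test on 124 |
|---|---|---|---|
| 0.3 | 0.65 | 35% | 124 × 0.65 ≈ 81 |
| 0.5 | 0.75 | 25% | 124 × 0.75 = 93 |
| 0.7 | 0.85 | 15% | 124 × 0.85 ≈ 105 |
| 0.9 | 0.95 | 5% | 124 × 0.95 ≈ 118 |

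Simulating 20,000 trials with 62 per arm gave 0.66, 0.76 and 0.86 at r = 0.3, 0.5 and 0.7.

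**NOSE with a narrowed baseline** (assumed sb = 12, sf = 25, because entry requires a score of at least 55). At r = 0.2, for example, the change-score variance is 144 + 625 − 120 = 649, the ANCOVA variance is 625 × 0.96 = 600, and the ratio is 0.924.

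| r | ratio | variance saved | slope b = r × 25/12 |
|---|---|---|---|
| 0.2 | 0.924 | 7.6% | 0.42 |
| 0.3 | 0.966 | 3.4% | 0.63 |
| 0.4 | 0.992 | 0.8% | 0.83 |
| 0.5 | 0.999 | 0.1% | 1.04 |
| 0.6 | 0.978 | 2.2% | 1.25 |
| 0.7 | 0.913 | 8.7% | 1.46 |

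**Other SD ratios.** With sb/sf = 0.5 the variance ratio is 0.958, 1.000 and 0.927 at r = 0.3, 0.5 and 0.7. With sb/sf = 0.75 it is 0.818, 0.923 and 0.995. The gain vanishes only where the slope equals 1.

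**Chance imbalance.** With 62 per arm, a baseline difference of 1.96 standard errors is 1.96 × √(2/62) = 0.35 SD.

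- Equal SDs, so b = r: the shift is (1 − r) × 0.352 = 0.25, 0.18 and 0.11 SD at r = 0.3, 0.5 and 0.7. It favours the arm that starts worse.
- NOSE as assumed above: d = 0.352 × 12 = 4.2 points. The shift is (0.417 − 1) × 4.22 = −2.5 points at r = 0.2 and (1.458 − 1) × 4.22 = +1.9 points at r = 0.7. A higher NOSE score is worse, so the sign reverses across the range: the arm that starts worse looks better at low r and worse at high r.

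In the equal-SD simulation the change-score effect correlated −0.59, −0.50 and −0.38 with the chance baseline difference at r = 0.3, 0.5 and 0.7. The ANCOVA effect correlated between 0.00 and 0.01.

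**Cost of the covariate.** The approximate variance cost is 1/(N − 4): 1/56 = 1.8% at N = 60 and 1/120 = 0.8% at N = 124.

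**The case against.** The strongest reply is that nothing here is an error. The t-test is prespecified, simple and valid. The endpoints are secondary, with no power target, no share of alpha and no success criterion. For NOSE, the trial's main instrument, the gain may be close to nil: at r = 0.4 or 0.5 it is smaller than the 1.8% cost of the covariate at 60 subjects. The 15-35% for the other scales assumes equal SDs. Entry also requires a NOSE score of at least 55, a positive modified Cottle manoeuvre and failed medical management, which may narrow the baseline breathing VAS as well and pull its gain towards the NOSE range. A large baseline imbalance would at least be visible in the SAP 5.4.1 tables.

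Most of this stands, and it limits the point to an improvement in efficiency. It does not remove it. A visible imbalance is still not adjusted for, and the possible loss from adding the covariate is a percent or two against a possible gain many times larger.

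A reader might infer more than the documents support:

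- That the analysis ignores baseline. It does not: baseline is subtracted from every value.
- That the treatment effect is biased. Under 1:1 randomisation it is unbiased, with valid type I error. The shift is conditional on the baseline difference that happens to occur.
- That the arm starting worse must look better. That holds only for a slope below 1, and under the NOSE assumptions above the slope exceeds 1 from r = 0.5 upward.

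**Conclusion.** The point holds as a near-free improvement to secondary analyses, not as the correction of an invalid test. That ANCOVA is at least as precise in large samples is certain. The size of the gain is not, because it depends on SDs and correlations that the documents do not supply. On the assumptions shown, it is about 0-9% less variance for NOSE. For VAS, ESS and PSQI it is 15-35% with equal SDs and r of 0.3-0.7, falling to 5% at r = 0.9 and towards zero if the baseline is narrowed. The responder test, the 124 evaluable subjects and the group-sequential boundaries do not depend on it.

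**What to change.** Amend SAP 5.3 by the route in SAP 5.4.3, before unblinded comparative data are seen:

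- For the randomised comparisons at 7 days, 30 days and 3 months, analyse NOSE, VAS, ESS and PSQI by ANCOVA, with the follow-up score as outcome and arm and the baseline value of the same scale as covariates. Using the change score as outcome in this model gives the same treatment estimate, so the endpoint definitions can stay.
- Report the adjusted mean difference with its model-based 95% CI. SAP 5.1 now leaves the interval for the difference optional.
- Keep the two-sample t-test as a check.

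The cost is a sentence or two in the SAP, one model statement in SAS and one degree of freedom, roughly 1-2% of variance at 60 to 124 subjects. No new data are needed.
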